9 DATA AND SAFETY MONITORING

9.1 Safety Monitoring

Principal investigator: Accrual, efficacy and safety data will be monitored by the PI.

NHLBI IRB: Accrual and safety data will be reviewed annually by the Institutional Review Board (IRB). Prior to implementation of this study, the protocol and the proposed consent form will be reviewed and approved by the properly constituted Institutional Review Board (IRB) operating according to the Title 45 CFR 46. This committee must approve all amendments to the protocol or informed consent, review all SAEs, and conduct continuing annual review so long as the protocol is open to accrual or follow up of subjects.

9.2 Event Characterization and Reporting

Events include adverse events (AE), serious adverse events (SAE), protocol deviations (PD), unanticipated problems (UP), and non-compliance.

The principal investigator will review all events (AEs, protocol deviations, UPs, SAEs) to determine the seriousness, expectedness, and reportability of the event. As required and/or needed, the principal investigator will review the events with the Sponsor to make the final determination of seriousness and reportability.

9.2.1 Definitions

Adverse Event (AE): Any untoward or unfavorable medical occurrence in a human subject, including any abnormal sign (e.g., abnormal physical exam or laboratory finding), symptom, or disease, temporally associated with the subject's participation in the research, whether or not considered related to the research.

Serious Adverse Event (SAE): A serious adverse event that:

- results in death;
- is life-threatening (places the subject at immediate risk of death from the event as it occurred);
- results in in-patient hospitalization or prolongation of existing hospitalization;
- results in a persistent or significant incapacity;
- results in a congenital anomaly/birth defect; or
- based upon appropriate medical judgment, may jeopardize the subject's health and may require medical or surgical intervention to prevent one of the other outcomes listed in this definition.

Suspected adverse reaction: Suspected adverse reaction means any adverse event for which there is a reasonable possibility that the drug caused the adverse event. For the purposes of IND safety reporting, 'reasonable possibility' means there is evidence to suggest a causal relationship between the drug and the adverse event. A

suspected adverse reaction implies a lesser degree of certainty about causality than adverse reaction, which means any adverse event caused by a drug.

Serious event: An event is serious if it meets the definition of a serious adverse event (above) or if it requires immediate corrective action by a PI and/or IRB to protect the safety, welfare or rights of subjects.

Unexpected adverse reaction: An adverse event or suspected adverse reaction is considered “unexpected” if it is not listed in the investigator brochure or is not listed at the specificity or severity that has been observed; or, if an investigator brochure is not required or available, is not consistent with the risk information described in the general investigational plan or elsewhere in the current application. “Unexpected”, also refers to adverse events or suspected adverse reactions that are mentioned in the investigator brochure as occurring with a class of drugs or as anticipated from the pharmacological properties of the drug, but are not specifically mentioned as occurring with the particular drug under investigation.

Unanticipated Problem (UP): Any incident, experience, or outcome that meets all of the following criteria::

1. unexpected in terms of nature, severity, or frequency in relation to
 - a. the research risks that are described in the IRB-approved research protocol and informed consent document; Investigator’s Brochure or other study documents; and
 - b. the characteristics of the subject population being studied; and
2. related or possibly related to participation in the research; and
3. places subjects or others at a greater risk of harm (including physical, psychological, economic, or social harm) than was previously known or recognized.

Unanticipated Problem that is not an Adverse Event: An unanticipated problem that does not fit the definition of an adverse event, but which may, in the opinion of the investigator, involves risk to the subject, affect others in the research study, or significantly impact the integrity of research data. For example, report occurrences of breaches of confidentiality, accidental destruction of study records, or unaccounted-for study drug.

Protocol Deviation (PD): Any change, divergence, or departure from the IRB approved research protocol.

Non-compliance: The failure to comply with applicable NIH HRPP policies, IRB requirements, or regulatory requirements for the protection of human research. Noncompliance may be further characterized as:

1. Serious non-compliance: Non-compliance that:
 - a. Increases risks, or causes harm, to participants.
 - b. Decreases potential benefits to participants.
 - c. Compromises the integrity of the NIH HRPP.
 - d. Invalidates the study data.
2. Continuing non-compliance: Non-compliance that is recurring. An example may be a pattern of non-compliance that suggests a likelihood that, absent an intervention, non-compliance will continue. Continuing noncompliance could also include a failure to respond to IRB requests to resolve previous allegations of non-compliance.
3. Minor (non-serious) non-compliance: Non-compliance that, is neither serious nor continuing.

9.2.2 Adverse Events Management

. The AEs will be attributed (unrelated, unlikely, possibly, probably or definitely) to study medication and/or disease. AEs will be graded by severity utilizing CTC version 2.0. A copy of the criteria can be down-loaded from the CTEP home page at <http://ctep.cancer.gov/reporting/ctc.html>.

Abnormal laboratory findings used to evaluate the safety of this protocol regimen will be collected to include any change from laboratory assessments done prior to first dose of study medication that result in a progression to a grade 3 or 4 laboratory toxicity. The laboratory toxicities will be attributed (unrelated, unlikely, possibly, probably or definitely) to study medication and/or disease. They will be graded by severity utilizing CTC version 2.0.

Length of Adverse Event reporting: Adverse event collection will continue for 6 months after the last dose of Campath after which the events will be recorded in the medical record but not abstracted to toxicity tables. Serious adverse event reporting will continue as long as the subject remains on study.

9.2.3 Serious Adverse Events Management

Serious adverse events will be attributed as definitely (clearly related to the research), probably (likely related to the research), possibly (may be related to the research), unlikely (doubtfully related to the research) and unrelated (clear not related to the research).

Treatment related SAEs (TRSAEs) are those attributed as definitely, probably, or possibly. As detailed in section 8.5 stopping rules, only Death and any grade IV toxicities considered to be definitely related to alemtuzumab (Campath-1H®) will be monitored and considered for early stopping the study according to statistically determined criteria. [name], NIDDK will serve as the independent monitor who reviews the attribution of TRSAEs

Hospitalization (overnight admission) for routine supportive care (platelet or RBC transfusions) or admission from the NIH inpatient unit to the NIH ICU for routine monitoring will not be reported as a serious adverse event.

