9.2.4.1 Reporting Timeframes to IRB Chair, Clinical Director, and/or NHLBI IRB

Serious Events

Reports to the IRB and CD: The PI must report Serious UPs, and Serious PDs to the IRB and CD as soon as possible but not more than 7 days after the PI first learns of the event using the NIH Problem Report Form.

Reports to the IRB Chair and CD: The PI must report all SAEs that do not meet the definition of UP to the IRB chair and CD not more than 14 days after the PI first learns of the event, using the NIH Problem Form.

Non-serious Events

Reports to the IRB and CD: The PI must report all UPs that are not Serious to the IRB and CD, and PDs that are not Serious to the IRB, not more than 14 days after the PI first learns of the event using the NIH Problem Form.

Deaths

The PI must report all deaths (that are not UPs) to the CD as soon as possible, but not more than 7 days after the PI first learns of the event

9.2.4.2 At continuing review, the PI will provide to the IRB a summary of:

- All UPs
- All PDs
- All AEs (except for those granted a waiver of reporting)
- If, while preparing the continuing review, the PI identifies a greater frequency or level of severity of expected adverse events than was previously identified in the protocol or investigational brochure (IB), these should be reported separately as a UP. If such an observation occurs before the time of continuing IRB review, it should be reported to the IRB and CD as a UP in the time frames noted above, and summarized at the time of continuing review.

Exclusions to data reporting:

The following Adverse Events will be captured only in the source documents and will not be reported to the IRB at the time of continuing review.

- Laboratory values that do not meet the definition of AE
- All grade 1 events listed as expected in the investigator's brochure, package insert or the protocol.

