Cardiac toxicities: The following were reported in at least one patient treated on studies where alemtuzumab was used as a single agent: cardiac failure, cyanosis, atrial fibrillation, cardiac arrest, ventricular arrhythmia, ventricular tachycardia, angina pectoris, coronary artery disorder, myocardial infarction, and pericarditis. Some of these cardiac abnormalities may be irreversible. For this reason, we will monitor subjects with an echocardiogram and a 24 hour Holter monitor before treatment begins and after the last dose of alemtuzumab (Campath®). The ECHO will also be repeated at the 3 month follow up visit. We will closely monitor subjects for cardiac symptomology and ask them to immediately report any cardiac symptoms (palpitations, irregular pulse, difficulty in breathing, dizziness, swelling in the ankles, chest discomfort or pain).

Hematologic toxicities: Myelosuppression involves all 3 cell lineages. Serious and in rare instances fatal pancytopenia/marrow hypoplasia, autoimmune idiopathic thrombocytopenia, and autoimmune hemolytic anemia have occurred in patients receiving alemtuzumab (Campath®).

Other side effects (> 5% in CLL studies) include headache, anorexia, asthenia, skeletal pain, myalgias, peripheral edema, dyesthesias, dizziness, tremor, stomatitis, mucositis, dyspnea, cough, pneumonitis, rhinitis, abdominal pain, back pain, dyspepsia, constipation, insomnia, depression, somnolence, diarrhea, and EBV related lymphoproliferative disease.

Pregnancy and breast feeding: Animal reproductive studies have not been conducted. It is not known whether alemtuzumab can affect reproductive capacity or cause fetal harm. Human IgG is known to pass the placental barrier and thus may potentially cause fetal B-cell depletion; therefore alemtuzumab should only be given to pregnant women only if clearly needed. It is not known whether alemtuzumab is excreted in human milk. Because human IgG is excreted in human milk and the potential for absorption and immunosuppression in the infant is unknown, women should be advised to discontinue nursing for at least 3 months following last dose of alemtuzumab (Campath®).

10.3.2 Related to bone marrow aspirate and biopsy: No major risks are involved with bone marrow aspirate and biopsy. However, a small risk of infections, pain, bleeding, and hematoma formation at the site of the aspiration exists with the procedure.

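### The SAE exemption for overnight transfusion admissions in 9.2.3 is not limited by baseline transfusion need or by attribution, and routine is undefined

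*Combined protocol and SAP*

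**What the plan says.** Among the grounds that make an event serious, section 9.2.1 includes one that "results in in-patient hospitalization or prolongation of existing hospitalization". It also lists an event that "is life-threatening (places the subject at immediate risk of death from the event as it occurred", and, on medical judgment, one that may endanger the subject and "may require medical or surgical intervention to prevent one of the other outcomes listed in this definition".

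Section 9.2.3 then carves out "Hospitalization (overnight admission) for routine supportive care (platelet or RBC transfusions) or admission from the NIH inpatient unit to the NIH ICU for routine monitoring" and states that these "will not be reported as a serious adverse event". The carve-out mentions neither transfusion history nor cause. Its bracket names the two blood products but does not say what makes their use routine.

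Two consequences hang on SAE status. Section 9.2.4.1 says "The PI must report all SAEs that do not meet the definition of UP to the IRB chair" and the Clinical Director, within 14 days. Section 9.2.3 appoints an independent monitor to review the attribution of TRSAEs, which it defines as SAEs judged possibly, probably or definitely related.

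Under 9.2.2, adverse events are collected until six months after the last dose. Later ones go into the medical record but not the toxicity tables. SAE reporting continues for as long as the subject is on study.

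**The concern.** In a cytopenic population it is sensible not to file an SAE each time a transfusion-dependent subject stays overnight for blood. The sentence goes further than that purpose. It applies equally to a subject who had never needed blood or platelets and first needs them after alemtuzumab.

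For that subject the admission may be the first sign of a harm the protocol itself describes: "Serious and in rare instances fatal pancytopenia/marrow hypoplasia, autoimmune idiopathic thrombocytopenia, and autoimmune hemolytic anemia have occurred in patients" receiving the drug. If the overnight stay is the only ground for seriousness, the rule as written takes away both the expedited report and the independent look at causality. What remains is the investigator's own attribution. The loss is in the speed and independence of safety review. The efficacy result is not affected.

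**Working it through.** The plan gives no figure on this point to reproduce, so the check sets the provisions side by side.

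1. **Can a subject with no transfusion need enrol?** Yes. Section 4.1.3 requires one or more of its cytopenia criteria, and neutrophils below 500/µL suffice alone. Only one alternative within the anemia criterion refers to transfusion (more than 2 RBC units a month for two months).

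2. **Could the drug create the need?** Section 10.3.1 gives anemia 80% and thrombocytopenia 72%, and names marrow hypoplasia and immune loss of platelets and red cells. These show that the harm is recognised. They do not give its rate under this regimen. The neighbouring infection rates match the CLL trial in 2.3.3.2: sepsis 14/93 = 15.1% (15% stated) and CMV 7/93 = 7.5% (8% stated). The cytopenia rates therefore probably come from CLL experience too, and that trial used 30 mg three times weekly for up to 12 weeks.

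3. **What happens to each type of event?**
   - New cytopenia that is life-threatening, or medically important in the investigator's judgment: still an SAE under 9.2.1 on that other ground. It is reported and, if at least possibly related, goes to the monitor.
   - New transfusion admission, possibly related, serious only through the overnight stay, within six months of the last dose: exempt under 9.2.3. It remains an adverse event. A worsening from pre-dose values to grade 3 or 4 is collected and attributed by the investigator (9.2.2), and adverse events are summarised to the IRB at continuing review (9.2.4.2). There is no routine 14-day SAE report, and no independent review under the 9.2.3 definition.
   - The same admission more than six months after the last dose: still exempt as an SAE, and no longer abstracted to the toxicity tables. Follow-up runs to five years (sections 3 and 6.5), so for a single-cycle subject this covers roughly 60 − 6 = 54 months, with scheduled blood counts only annual after the six-month visit.
   - Transfusion need already present before dosing, admission unrelated to the drug: exempt, as the sentence presumably intends.

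4. **Does the exemption alter the stopping rule?** No. Section 8.5 counts deaths and grade IV toxicities definitely related to alemtuzumab, leaving out temporary cytopenias. Neither admission nor SAE status enters that definition, so a lasting, definitely related grade IV cytopenia counts either way.

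5. **Which events does the monitor see?** The abbreviation TRSAE has two meanings. In 8.5 it stands for treatment related severe adverse events of the two types just described. In 9.2.3 it means SAEs at least possibly related. On the 8.5 meaning, a lasting, definitely related grade IV cytopenia would reach the monitor regardless of how the admission was classed. An event of lower grade, or one judged only possibly or probably related, would not. On the 9.2.3 meaning, an event must first be an SAE.

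**The case against.** The strongest reply is that the exemption removes one kind of hospitalization and leaves every other SAE criterion in force. The grave harms in 10.3.1 are the ones most likely to be life-threatening or medically important, and an investigator may fairly decide that a first transfusion for a drug-caused cytopenia is not routine. A reader might infer that drug-caused cytopenias escape SAE reporting altogether. The documents do not support that.

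Nor are the milder events hidden. Blood counts are weekly to three months and then every other week to six. A higher frequency or severity of expected events than previously identified must be reported as an unanticipated problem (9.2.4.2). The background also gives reason to expect few events: in the 21-patient series at 10 mg for 10 days, treatment was well tolerated apart from first-dose reactions (2.3.3.4), and in the CLL trial neutrophils and platelets recovered by two months of follow-up (2.3.3.2).

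All of this stands, and it narrows the point. It does not close it. The remaining routes carry investigator attribution with no stated independent review, adverse event abstraction stops at six months, and everything turns on an undefined word. The opening text of 9.2.4, before 9.2.4.1, was not available for this check, so a further reporting provision there cannot be excluded.

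**Conclusion.** The point holds in a limited form. It concerns new transfusion admissions, possibly or probably related to alemtuzumab, for which the overnight stay is the only ground for seriousness and which the investigator treats as routine. Followed as written, the plan does not require an SAE report or, under the 9.2.3 definition, independent attribution review for these. Beyond six months from the last dose they also drop out of the toxicity tables. Definitely related events are in the same position unless they fall under the 8.5 definition.

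The number of such events cannot be derived. The documents do not say how many of the 39 planned subjects will enter without transfusion need, or how often this regimen leads to a first transfusion admission. A reader might set a guessed count against the stopping boundaries of 3 to 7. That comparison is not supported: those boundaries count deaths and definitely related grade IV toxicities, and a transfusion admission need be neither. A reader might also infer that the exemption keeps events out of the stopping rule. Section 8.5 does not depend on SAE status, so it does not. No defect is shown in the ICU clause of the same sentence.

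This is a worthwhile, low-cost tightening of safety reporting. It does not threaten the trial's conclusions.

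**What to change.** Amend the exemption in 9.2.3 so that an overnight platelet or RBC transfusion admission goes unreported as an SAE only when both conditions hold: the subject already needed that product before the first dose, and the admission is not attributed as possibly, probably or definitely related to alemtuzumab. Assess all other overnight transfusion admissions as SAEs under 9.2.1 and, if at least possibly related, send them to the independent monitor.

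Using attribution as the second condition is better than making every rise over the baseline rate an SAE. The latter would also sweep in non-response and disease progression.

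The cost is a few more SAE reports and a baseline record of transfusion need for each product. That record is not fully in place: the two-month look-back in 4.1.3 covers RBC units in one entry route only, no platelet equivalent is given, and 6.1 does not list transfusion history separately from the medical history. It would also serve the transfusion-independence endpoint in 8.2.1. No new tests and no change to clinical care are involved.

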9.2.4.1 Reporting Timeframes to IRB Chair, Clinical Director, and/or NHLBI IRB

Serious Events

Reports to the IRB and CD: The PI must report Serious UPs, and Serious PDs to the IRB and CD as soon as possible but not more than 7 days after the PI first learns of the event using the NIH Problem Report Form.

Reports to the IRB Chair and CD: The PI must report all SAEs that do not meet the definition of UP to the IRB chair and CD not more than 14 days after the PI first learns of the event, using the NIH Problem Form.

Non-serious Events

Reports to the IRB and CD: The PI must report all UPs that are not Serious to the IRB and CD, and PDs that are not Serious to the IRB, not more than 14 days after the PI first learns of the event using the NIH Problem Form.

Deaths

The PI must report all deaths (that are not UPs) to the CD as soon as possible, but not more than 7 days after the PI first learns of the event

9.2.4.2 At continuing review, the PI will provide to the IRB a summary of:

- All UPs
- All PDs
- All AEs (except for those granted a waiver of reporting)
- If, while preparing the continuing review, the PI identifies a greater frequency or level of severity of expected adverse events than was previously identified in the protocol or investigational brochure (IB), these should be reported separately as a UP. If such an observation occurs before the time of continuing IRB review, it should be reported to the IRB and CD as a UP in the time frames noted above, and summarized at the time of continuing review.

Exclusions to data reporting:

The following Adverse Events will be captured only in the source documents and will not be reported to the IRB at the time of continuing review.

- Laboratory values that do not meet the definition of AE
- All grade 1 events listed as expected in the investigator's brochure, package insert or the protocol.

9.3 Data management

The PI will be responsible for overseeing entry of data into an in-house password protected electronic system and ensuring data accuracy, consistency and timeliness. The principal investigator, associate investigators, Hematology Branch fellows, research nurses and/or a contracted data manager will assist with the data management efforts. Data will be abstracted from Clinical Center progress notes as well as from progress notes forwarded from home physician. Laboratory data from NIH will be imported electronically from CRIS into an in-house clinical trial database. Laboratory values from referring home physicians will be entered into the system.

End of study procedures: Data will be stored in locked cabinets and in a password protected database until it is no longer of scientific value.

Loss or destruction of data: Should we become aware that a major breach in the our plan to protect patient confidentiality and trial data has occurred, the IRB will be notified.

Publication Policy: Given the research mandate of the NIH, patient data including the results of testing and responses to treatment will be entered into an NIH-authorized and controlled research database. Any future research use will occur only after appropriate human subject protection institutional

approval such as prospective NIH IRB review and approval or an exemption from the NIH Office of Human Subjects Research Protections (OHSRP).

